Serum Biochemical Parameters. Blood draws and laboratory analysis will be performed by the Center for Clinical and Translational Science (CCTS). Blood specimens may also be obtained in tubes by the dialysis staff, for pick up by the coordinators, at the time the patient is receiving dialysis to minimize additional patient venipuncture. Serum calcium will be measured using routine laboratory technique (Roche autoanalyzer). Plasma intact and 1-84 PTH levels will be measured by a radioimmunoassay (Scantibodies, Santee, CA). The intra- and interassay coefficients of variation for intact PTH are <5 and <7%, and for 1-84 PTH <6 and <8%. BSAP levels will be measured using an EIA (Metra BAP EIA, Quidel, San Diego, CA). The intra- and inter-assay coefficients of variation are <6% and <8%. TRAP-5b levels will be determined using an EIA (MicroVue, Quidel, Santa Clara, CA). The intra- and inter-assay coefficients of variation are <2.2% and <3%. P1NP levels will be measured using an ELISA (USCNK, Wuhan, China); the intra- and inter-assay coefficients of variation are <9% and <10%. Serum sclerostin levels will be measured using an EIA (Tecomedical group, Sissach, Switzerland). The intra- and inter-assay coefficients of variation are <3.1% and <3.5%. Serum FGF23 levels will be measured by an ELISA (EMD Millipore, Billerica, MA). The intra- and inter-assay coefficients of variation are <8% and <12%. DKK1 will be determined by an ELISA (Biomedica, Vienna, Austria). The intra- and inter-assay coefficients of variation are <8% and <12%. Bone mineral density (BMD) Two techniques—DXA and QCT—will measure BMD. DXA measurements will be performed in the CCTS core facility. QCT measurements will be conducted in the UK Department of Radiology and qualitatively analyzed on a Syngo MMWP workstation and quantified in the Image Analysis Lab of the Division of Nephrology, Bone and Mineral Metabolism. Measurements will be performed using FDA approved imaging equipment, calibration phantoms, and post imaging analysis software/clients used in everyday clinical practice. (The medical center is on a regular schedule of equipment upgrades and, consequently, the specific equipment utilized will change periodically.) Imaging equipment will be maintained and calibrated using manufacturer recommended techniques and schedules. The studies will be performed under the supervision of, and interpreted by, board certified physicians.

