Patients consenting for baseline measurements will have BMD measurements of the total hip, lumbar spine and radius by DXA and total body scan. We do not use QCT for initial BMD assessment to avoid unnecessary radiation exposure to patients with normal bone mass who will be excluded from the study. Patients who are not do not have low bone densityosteoporotic by DXA T-scores/Z-

scores at any site will be excluded from further participation. Results from our prior funding period study indicate this will be 30% or 178 patients. Those patients who are identified as having low bone density/osteoporotic will have blood draws performed for determination of turnover status (PTH, PTH ratio and TRAP-5b; see Table 1) and baseline biochemical results (serum calcium and BSAP). They will also have BMD measurements of the total hip and spine by QCT, and CAVC measured by MDCT. Patients will be assigned to one of two treatment arms based on their turnover status: 1) low turnover patients and 2) normal or high turnover patients. For each treatment arm we will use adaptive randomization by group completion rates, age race and gender to assign patients to one of two groups A) treatment, and B) no study treatment (standard of care) controls.

For the extension of treatment modification, we will contact all patients who completed one year in either the treatment or control arms. Patients who previously participated in the treatment arm will be offered an additional 1 year of therapy to complete 2 years of therapy. For patients who previously participated in the control arm, they will be offered 2 years of therapy. Both therapies can be given in two consecutive years, or with a time-gap in-between.

TREATMENT PROTOCOLS:

Low Turnover Groups: Patients with low bone turnover will be randomized to receive daily teriparatide injections with cinacalcet or no study treatment, i.e. standard of care, as controls.

Normal or High Turnover Groups: Patients with normal or high bone turnover will be randomized to receive alendronate or no study treatment, i.e., standard of care, as controls. Teriparatide is not justified in these patients because it might worsen underlying high turnover abnormalities and requires avoidable daily injections.

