Table 2. Detail of Blood Draws for Monitoring Safety and Compliance and Secondary Endpoint Serum Biochemical Parameters
Teriparatide

Treatment Group Base-line Bi-weekly visits until steady state Q1 Visit Q2 Visit Q3 Visit 1 Year 15 mo 18mo 21mo 2 yr
or Safety: Serum Calcium & PTH X X X X X X X X X X X X

For Compliance: BSAP X X X X X X X X X X

Secondary Endpoints: FGF23, P1NP, Sclerostin, DKK-1 & PTH Ratio X X X X X

Alendronate

Treatment Group Base-line Monthly visits until steady state Q1 Visit Q2 Visit Q3 Visit 1 Year 15 mo 18mo 21mo 2yr

For Safety and Compliance: BSAP X X X X X X X X X X

Secondary Endpoints: Serum Calcium, PTH & PTH Ratio, FGF23, P1NP, Sclerostin, DKK-1 X X X X X

Standard of Care Controls Base-line Q2 Visit 1 Year 15mo 18mo 21mo 2 yr

Secondary Endpoints: All of the above Serum Biochemical Parameters X X X X X

Cinacalcet will be adjusted in 30 mg steps up to a maximum daily dose of 180 mg if needed to keep intact PTH at levels less than 200 pg/mL. If by six weeks, this fails to achieve PTH levels less than 200 pg/mL, patients will be excluded from further study participation. In the rare case where PTH level maintenance requires cinacalcet doses that induce serum calcium levels below 8.5 mg/dL, treatment will cease for two weeks after which calcium will be re-measured. At two weeks if calcium remains below 8.5 mg/dL, patients will be excluded from further participation in the study. If calcium is normalized, cinacalcet will be reinstated at half of the prior dose. Calcium will be checked again at the next monitoring visit. If at any measurement point PTH levels are less than 60 pg/mL cinacalcet will be withheld and reinstated if levels are again above 200 pg/mL.

Treatment Protocol for Alendronate: Patients with normal or high bone turnover will receive a starting dose of 35 mg alendronate p.o. once per week. Patients will be carefully instructed to follow the manufacturer's recommendations for administration. Serum calcium will be rechecked 1 week +/- 3 days after starting therapy. Dosage will be adjusted according to changes in the bone turnover marker

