BSAP from blood drawn at monthly monitoring visits for the first 3 months, thereafter at quarterly monitoring visits. BSAP is expected to go down, but to avoid over-suppression, will not be allowed to go below the low normal range of the assay, as is done clinically. Our data show that mid/normal ranges of these markers in CKD-5D patients indicate low turnover^{48, 49} If this safety threshold is crossed, treatment will be stopped until values are back above the threshold at a regularly scheduled monitoring visit. Once demonstrably back within safety threshold, treatment will be reinstated at half of the initial dose (35 mgs every other week). If BSAP does not go down at least 8% over a one month period, treatment doses will be doubled to 70 mgs per week. If they still remain high, study coordinators will carefully review with the patients the mode of drug intake and possible compliance lapses.

Primary Endpoint At one year after baseline, we will assess bone mass using QCT BMD measurements of the total hip and compare 1 and 2 year changes in bone mass between the treatment and control groups. Total hip will be used as the primary endpoint site because in our prior funding period we showed that changes at the total hip in QCT BMD are more pronounced than at the spine⁶. The Secondary endpoint will be differences between the treatment and control groups in changes in coronary artery calcifications by MDCT. This will be relevant regardless of bone effects.

Other secondary endpoints tracked at baseline, 6 months, and 1 year, 18 and 24 months will include serum biochemical markers of bone activity; FGF 23, BSAP, TRAP5b, P1NP, Sclerostin, and DKK1.

Additionally we will record 1) Change in QCT BMD of the spine to compare with the hip) 2) Changes in DXA BMD of the hip and spine (to determine whether the more commonly available DXA results are equivalent to QCT and 3) Changes in aortic and heart valve calcification (to compare with the coronary artery calcifications).^{50,51} 4) Whole body composition (%fat vs %lean) as it relates to survival in CKD-5D patients.

Attachments

Attach Type	File Name
ResearchProcedures	figure 3 7.22.2019 pdf.pdf

Data Collection: List the data or attach a list of the data to be collected about or from each subject (e.g. interview script, survey tool, data collection form for existing data).

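### The alendronate doubling rule has no BSAP level condition of its own, and baseline BSAP is not compared with the plan's stop limit before the first dose

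*Combined protocol and SAP*

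**What the plan says.** All dosing rules for this stratum stand in Research Procedures, Treatment Protocol for Alendronate. The starting dose is 35 mg once weekly. BSAP is then measured monthly for three months and quarterly after that.

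- **Stop rule.** BSAP "will not be allowed to go below the low normal range of the assay, as is done clinically". If it does, alendronate is withheld until a scheduled visit shows recovery, and then "treatment will be reinstated at half of the initial dose (35 mgs every other week".
- **Reading of the marker.** The same paragraph adds: "Our data show that mid/normal ranges of these markers in CKD-5D patients indicate low turnover".
- **Doubling rule.** "If BSAP does not go down at least 8% over a one month period, treatment doses will be doubled to 70 mgs per week". The sentence names no BSAP level. The next one asks for a review of drug intake and compliance if values stay high; it does not define high.

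At screening, patients with low bone density have blood drawn for "determination of turnover status (PTH, PTH ratio and TRAP-5b; see Table 1) and baseline biochemical results (serum calcium and BSAP". BSAP is thus collected at baseline but listed apart from the tests that decide turnover status. In Table 2 the alendronate block is headed "Treatment Group Base-line Monthly visits until steady state" and carries a row "For Safety and Compliance: BSAP", so baseline BSAP belongs to the safety series. The inclusion and exclusion criteria contain laboratory conditions on serum calcium and calcidiol, and none on BSAP.

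**The concern.** The plan treats L as a safety threshold against over-suppression of bone turnover. Two parts of the dosing text do not respect it.

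First, escalation depends on change alone. A small fall from a BSAP just above L leads to the same doubling as a small fall from a very high BSAP. Only the second patient clearly has turnover left to suppress.

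Second, the limit is written for on-treatment values only. A patient whose baseline value is already under it meets no rule until month 1.

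The trial's premise is that treatment should match turnover, with alendronate reserved for normal or high turnover. As written, the plan can raise the dose of an antiresorptive, or start it, in a patient whose latest BSAP points by the plan's own account to low turnover. Potential Risks also says that alendronate is not recommended at GFR below 35 mL/min, so these patients are treated outside the usual recommendation and the guard rails should be exact.

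**Working it through.** **Inputs.** L is the lower normal limit of the BSAP assay; the protocol gives no number, so levels are shown as multiples of L. Start 35 mg weekly, doubled dose 70 mg weekly, restart 35 mg every other week, monthly checks to month 3 (Treatment Protocol for Alendronate). BSAP inter-assay CV below 8% (Study Design, Serum Biochemical Parameters). The 8% criterion is described as assay error in Treatment Protocol for Teriparatide.

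**Step 1: are the doses coherent?** 2 × 35 = 70 mg per week; 35 / 2 = 17.5 mg per week on restart. Both agree with the text.

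**Step 2: apply both rules to the same reading.** Let B be the previous BSAP and f the one-month fall. The new value is B(1 − f). Stop if it is below L; double if f < 8%.

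| Previous | Fall | New value | Stop? | Double? |
|---|---|---|---|---|
| 1.03L | 2% | 1.03 × 0.98 = 1.009L | no | yes |
| 1.10L | 5% | 1.10 × 0.95 = 1.045L | no | yes |
| 1.50L | 5% | 1.50 × 0.95 = 1.425L | no | yes |
| 1.05L | 5% | 1.05 × 0.95 = 0.9975L | yes | yes |

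In the last row both conditions hold. The stop rule is the sensible reading there, and no conflict is claimed. In the first three rows doubling is the only instruction. For any B at or above L / 0.92 = 1.087L, a fall under 8% always leaves the patient at or above L, so the doubling rule acts alone. For B between L and 1.087L it depends on the size of the fall.

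**Step 3: compare two patients at the same level.** One reads 1.009L after a stop and restarts at 17.5 mg per week on average. Another reads 1.009L after a small fall and goes to 70 mg per week. The same BSAP leads to doses that differ by 70 / 17.5 = 4 times.

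**Step 4: exposure per affected patient, at four weeks per month.** Baseline below L: 4 × 35 = 140 mg before the first BSAP check. Doubled at month 1: 4 × 70 = 280 mg instead of 140 mg before the next check.

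**Step 5: how well does an 8% fall identify non-response?** Take the observed ratio as (1 − true fall) times log-normal error in two readings, with s² = ln(1 + CV²) per reading and no biological variation (none is given). Then P(observed fall < 8%) = 1 − Φ[(ln 0.92 − ln(1 − true fall)) / (s√2)]. For a true fall of 10% this is 42% at CV 8%, 40% at CV 6% and 35% at CV 4%. Some patients doubled near L would therefore be responding already, which is a reason to add a level condition.

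**Step 6: reference points for a floor.** Room for a further fall of exactly 8% needs L / 0.92 = 1.087L, with nothing left for assay error. Adding one-sided 95% assay error in one reading gives exp(1.645 × 0.08) / 0.92 = 1.24L at CV 8%, or 1.20L at CV 6%.

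**The case against.** **A lower bound exists.** A reader might infer that alendronate can be escalated with no lower BSAP limit at all. The documents do not support that: the stop rule applies at every dose. What stands is narrower. The stop rule acts only after L has been crossed on treatment, so it prevents neither doubling just above L nor a first dose below it.

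**Doubling was meant for high values.** The sentence after the doubling rule speaks of values that are still high, which suggests this intent. It governs only the step after doubling, however, and sets no level. If that was the intent, a stated floor would put it in writing.

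**The plan asks for no second 8% fall.** It is tempting to say that the rule seeks a further 8% drop after doubling and so drives a patient at 1.009L to 0.929L. The text does not say this; the step after doubling is a compliance review. The 1.087L figure is therefore only a reference point for a floor.

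**Treatment loss cannot be blamed on doubling.** A reader might also infer that doubling costs treatment, because a patient pushed below L restarts at half dose. But if 1.009L is the true level, a single reading falls below L with probability Φ(−ln 1.0094 / CV), about 45% at CV 8% and 44% at CV 6%, with no dose change at all. Such a patient may be stopped either way.

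**The harm evidence is thin.** The statement that adverse effects rise with dose closes a paragraph mainly on gastrointestinal effects and applies to every doubled patient. The harms that the plan ties to over-suppression are described as rare (jaw osteonecrosis) or as following more than five years of use (femoral fractures). This stands, and it keeps the point minor.

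**The missing rule may be elsewhere.** Table 1 and the figure attached to Research Procedures were not available to this review. The finding on baseline BSAP holds for the available text only.

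**Conclusion.** The point holds as a minor gap in the dosing text. The doubling rule has no level condition of its own, so it applies just above L and in the range that the plan reads as low turnover. In the text available, baseline BSAP is not compared with L before the first dose. Both follow from the wording and depend on no statistical assumption.

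The number of patients affected cannot be derived without a BSAP distribution. It is probably small, because the stratum is selected for normal or high turnover. Monthly checks limit exposure to about 140 mg (start below L) or 280 mg (doubled at month 1) before the next reading in the first three months; after that, checks are quarterly. No clinical harm has been quantified, and neither the power nor the primary comparison is called into question.

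**What to change.** 1. **Baseline check.** Before randomisation in the normal/high turnover stratum, require baseline BSAP at or above L, identically for alendronate and control patients. If it were applied only to treated patients after assignment, non-starters would arise in one group only. Apply the same check before a former control starts alendronate in the extension.
2. **Level condition on doubling.** Double to 70 mg weekly only if the one-month fall is under 8% and current BSAP is above a stated level clearly above L; otherwise keep 35 mg weekly. Mid-normal would fit the plan's own statement about the marker. The 1.087L figure is only the arithmetic minimum, and 1.24L adds an allowance for assay error at the 8% CV limit. The investigators should choose one level and state it.

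**Cost.** No new test or visit: baseline BSAP is already drawn before treatment consent. The change is one entry criterion of the same kind as those for calcium and calcidiol, and one clause in the dosing paragraph. A few patients become ineligible, some possibly after their baseline scans, since the scans belong to the same work-up. Some patients stay on 35 mg who would otherwise have been escalated, and more of them the higher the floor.

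### Alendronate is doubled on a missed BSAP fall before intake is checked, so a patient not taking 35 mg properly can first take the drug correctly at 70 mg weekly

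*Combined protocol and SAP*

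**What the plan says.** The rule is in Research Procedures, Treatment Protocol for Alendronate, of the combined protocol and SAP. Treatment starts at 35 mg once weekly, and "Patients will be carefully instructed to follow the manufacturer's recommendations for administration". Dosing then follows BSAP in this order:

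- **Missed response:** "If BSAP does not go down at least 8% over a one month period, treatment doses will be doubled to 70 mgs per week".
- **Continued non-response:** "If they still remain high, study coordinators will carefully review with the patients the mode of drug intake and possible compliance lapses".
- **Over-suppression:** BSAP "will not be allowed to go below the low normal range of the assay". If it does, treatment stops, and it restarts at 35 mg every other week once BSAP has recovered. This is the only dose reduction stated.

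The same section describes the monitoring as "BSAP from blood drawn at monthly monitoring visits for the first 3 months, thereafter at quarterly monitoring visits". The alendronate block of Table 2 heads the early visits differently, as "Monthly visits until steady state", and labels the marker "For Safety and Compliance: BSAP".

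Figure 3 (attached to Research Procedures) and the alendronate Study Drug Form (attached to Study Drug Information) are not reproduced in the document.

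**The concern.** Table 2 treats BSAP partly as a compliance marker, so a missed fall may mean that the drug was not taken, or not taken as instructed. The dosing rule raises the dose before asking which. If the cause is poor intake, the later review corrects it while the patient is already on 70 mg weekly. The dose has then been raised before 35 mg weekly was properly tried.

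At stake is an avoidable dose increase. Potential Risks says, in general terms and without figures, that adverse effects become more frequent as the dose rises. It also notes a recommendation against alendronate at GFR below 35 mL/min, and every participant here is on dialysis. No error rate, power figure or endpoint is involved.

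**Working it through.** **Order of steps in the two arms.** Under Treatment Protocol for Teriparatide, a missed 8% BSAP rise leads directly to a review of injection technique and compliance, and no dose increase is stated. Under Treatment Protocol for Alendronate, a missed 8% fall leads to doubling first and review second. The regimens differ, so the parallel is not exact, but it shows that the trial already has a review procedure triggered by a BSAP result.

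**Doses.** The plan's own figures reproduce: 2 × 35 = 70 mg weekly, and half the starting dose is 35 mg every two weeks, or 35 / 2 = 17.5 mg per week on average. The only written way down from 70 mg weekly is to stop after crossing the BSAP floor and then resume at an average of 17.5 mg per week. No step back to 35 mg weekly is written.

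**Exposure from coaching to the next BSAP check.** Inputs are the alendronate section's schedule (months 1, 2, 3, then 6, 9, 12) and the two doses. Assumptions: continued non-response is judged at the visit after doubling, coaching happens there, and intake is correct from then on. One month is 52 / 12 = 4.33 weeks, and a quarter is 13 weeks. Extra dose = (70 − 35) mg × weeks.

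| Doubled at | Coached at | Next BSAP check | Interval | Extra dose |
|---|---|---|---|---|
| Month 1 | Month 2 | Month 3 | 4.33 weeks | 35 × 4.33 = 152 mg |
| Month 2 | Month 3 | Month 6 | 13 weeks | 35 × 13 = 455 mg |
| Month 3 | Month 6 | Month 9 | 13 weeks | 35 × 13 = 455 mg |

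If Table 2's header keeps a non-responding patient on monthly visits, every row becomes 4.33 weeks and 152 mg.

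**Which row fits.** A patient who has not taken 35 mg properly from the start would ordinarily miss the fall at month 1, so the first row applies. The other rows need a patient who passed month 1 and failed later. Barring assay noise, that patient has shown some response at 35 mg, so 70 mg would not be the first properly taken dose.

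These figures run only to the next BSAP check. They are not total exposure at 70 mg, because no reduction at that check is stated unless the floor is crossed.

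**The case against.** The strongest reply is that titrating on a marker first, and reviewing intake if non-response continues, is a legitimate sequence with safeguards around it. Patients are instructed at the start. The BSAP floor stops treatment. Under Safety Precautions, gastrointestinal complaints bring counselling on intake, then a hold if they persist, and an end to participation if they recur. Persistent musculoskeletal pain brings a hold. Monthly contacts and weekly compliance meetings continue throughout. Potential Risks adds that adverse effects were usually mild when prescribing instructions were followed, and it cites a 12-week trial in 450 post-menopausal women with gastrointestinal effects of 13% on treatment against 11% on placebo.

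Much of this stands. The stop rules apply at 70 mg and limit the harm, and the patient in question is by then taking the drug as instructed. The cited trial is weaker support, since it was not in dialysis patients and its dose is not given. But none of these safeguards requires an intake check before doubling. Instruction precedes any lapse, the counselling depends on symptoms that a patient skipping doses may not have, the monthly contacts are for adverse events, and the weekly meetings are staff discussions.

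A reader might infer that 70 mg is unsafe as a first properly taken dose. The documents do not show that. A reader might also take 455 mg as the bound for a patient non-adherent from the start, but that figure belongs to a later failure on the quarterly schedule.

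**Conclusion.** The point holds as a minor dosing-safety matter. The order of steps allows an unneeded doubling when the real problem is intake, and the available text gives no route back to 35 mg weekly. For a patient non-adherent from the start, the size is about 4.3 weeks and 152 mg extra before the next BSAP check. It reaches 13 weeks and 455 mg only for a lapse first detected at month 2 or later with quarterly visits from month 3. These figures rest on the timing assumptions stated with the calculation.

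How often this would happen cannot be known from the documents. A reader might infer that the rule biases the randomised bone density comparison. It does not, because it is part of how the assigned treatment is delivered. Nor can it be said that the trial has no such rule anywhere, since Figure 3 and the Study Drug Form could contain one. The case for change is that an unneeded dose increase can be avoided at little cost.

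**What to change.** When a BSAP result misses the 8% fall, do and record the intake and compliance review already planned in the alendronate section before any dose change.

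- **When:** at the visit or, if the result comes later, by phone or at the next monthly contact provided for in Safety Precautions. BSAP is a laboratory immunoassay with no stated turnaround, so a same-visit decision cannot be assumed.
- **Intake was correct:** double to 70 mg weekly as now.
- **A lapse is found:** coach, keep 35 mg weekly, recheck BSAP at the next scheduled visit, and double only if the 8% fall is missed again.

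If Figure 3 or the Study Drug Form already says this, bring the alendronate section into line with it.

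The cost is a reordered rule, one adherence field in REDCap and a short interview, with a brief extra contact when results arrive after the visit. No extra blood draw is needed. For patients with a detected lapse, doubling waits one visit: one month for a failure at month 1 or 2, and up to a quarter from month 3. Some of these will be partial takers who would have needed 70 mg anyway. Self-report will miss some lapses, and those patients would be doubled as they are now.
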